11.1 Trial management group (TMG).....	42
11.2 Trial Steering Committee (TSC)	42
11.3 Data/safety monitoring committee (DMC).....	42
Appendix 1 – Main trial flow chart.....	43
Appendix 2 - Trial interventions summary table.....	44
Appendix 3 - Adverse event reporting summary	46
Appendix 4 - Sub-protocol for semi-structured interviews	47
Appendix 5 - Visual analogue scale	51
Appendix 6 - Trial Amendments.....	52
References.....	53

GLOSSARY OF ABBREVIATIONS

AE	Adverse Event
AR	Adverse Reaction
CI	Chief Investigator
CRP	C-Reactive Protein
CT	Computed Tomography
CTIMP	Clinical Trial of an Investigational Medicinal Product
CXR	Chest X-ray
DMC	Data/Safety Monitoring Committee
eCRF	Electronic Case Report Form
F	French
FEV1	Forced Expiratory Volume in 1 Second
f-LAT	Flexible Local Anaesthetic Thoracoscopy
FVC	Forced Vital Capacity
ICH GCP	International Conference for Harmonisation of Good Clinical Practice
ICMJE	International Committee of Medical Journal Editors
LAT	Local Anaesthetic Thoracoscopy (also known as pleuroscopy)
M, C+S	Microscopy, Culture and Sensitivity
NAAT	Nucleic Acid Amplification Techniques
NBT	North Bristol NHS Trust
NHS	National Health Service
P-A	Posterior-Anterior
PI	Principal Investigator
PPI	Patient and Public Involvement
REC	Research Ethics Committee
SAE	Serious Adverse Event
SAR	Serious Adverse Reaction
SUSAR	Suspected Unexpected Serious Adverse Reaction
TMG	Trial Management Group
tPA	Tissue Plasminogen Activator
TSC	Trial Steering Committee
TSP	Trial-Specific Procedure document
UK	United Kingdom
USA	United States of America
VAS	Visual Assessment Scale
VATS	Video-Assisted Thoracoscopic Surgery

1. STUDY SUMMARY

TITLE	Studying Pleuroscopy in Routine Pleural Infection Treatment (SPIRIT)		
DESIGN	Open-label, randomised, feasibility study (Non-CTIMP) with embedded qualitative interviews		
AIMS	To assess the feasibility and acceptability of randomising 30 patients to undergo either medical thoracoscopy or standard chest drain insertion for the treatment of pleural infection requiring drainage.		
PRIMARY OUTCOME	The feasibility of screening and enrolling patients into the study, and delivering the trial protocol		
INCLUSION CRITERIA	
 1. Suspected pleural infection, defined as an effusion (in the appropriate clinical context) with one or more of the following characteristics: 
 a. Fluid pH \leq7.20 or visually contains pus b. Pleural fluid glucose \leq3.4 mmol/L c. Positive bacterial or mycobacterial culture d. Positive gram stain or stain for acid-fast bacilli 2. Clinical team expect to be able to perform a medical thoracoscopy, if allocated, on either the same or the next day as the effusion is diagnosed as requiring drainage 3. Clinical team expect to be able to deliver the post-procedure trial schedule as detailed in the protocol 		
EXCLUSION CRITERIA	
 1. Any contraindication, in the opinion of the trial team or lead clinician, to 
 a. Medical thoracoscopy performed under conscious sedation b. Chest drain insertion c. Patient trial involvement 2. Research team unable to obtain, or patient unable/unwilling to provide, informed consent to trial participation 3. Thoracic imaging demonstrating fluid septation, loculation or position which would render medical thoracoscopy or standard medical management alone inappropriate, in the opinion of the trial team or lead clinician 4. Maximum pleural fluid depth of \leq2cm on thoracic ultrasound 5. Ongoing sepsis requiring haemodynamic support beyond basic fluid resuscitation 6. Previous pneumonectomy or lobectomy on the side of the effusion (or any ipsilateral thoracic surgery within six months) 7. Age $<$18 8. Pregnancy or lactation 9. Expected survival \leq3 months 		
FOLLOW-UP	3 months	SPONSOR	North Bristol NHS Trust

CHIEF INVESTIGATOR	[name]	FUNDER	The Academy of Medical Sciences
---------------------------	--------------------	---------------	---------------------------------

2. INTRODUCTION

2.1 BACKGROUND

2.1.1 Pleural infection epidemiology

Pleural infection is common, and can affect patients across a wide range of age groups. Incidence is highest in those who are either particularly old or young, with evidence to suggest that there are more cases year-on-year in children and adolescents, (1-3) perhaps as a result of childhood vaccination programmes altering host susceptibility profiles. (4) The increasing incidence appears to be an international phenomenon, with latest estimates suggesting there are at least 15,000 new cases in the United Kingdom each year, and approximately 80,000 cases in the UK and USA combined. (1) Hospital stays for such patients are often lengthy, with approximately one quarter requiring more than one month as inpatients. (2, 3, 5-7) Pleural infection patients also have a high risk of mortality (10-20%), which worsens in those who are more susceptible. (5, 7-9) Other than the old and young, at-risk populations include those who have chronic lung disease or diabetes; those with poor dentition or a higher-than-usual risk of aspiration; those who are immunosuppressed; or those with a history of drug or alcohol abuse. Chest trauma or medical intervention also predispose to pleural infection. (10, 11)

2.1.2 Pleural infection aetiology

Although primary pleural infection (without any evidence of lung parenchymal involvement) is increasingly recognised as an important condition, (12) the majority of patients will present having suffered a pneumonic illness in the build-up to their presentation. Up to 60% of patients with pneumonia will go on to develop an associated reactive fluid collection (parapneumonic effusion) around the lung, and around 10% of these go on to develop evidence of secondary infection. (13-15) The diagnosis of pleural infection can be made directly, by the demonstration of pus (empyema) or organisms in a pleural sample, or indirectly, when markers of high metabolic activity (such as a low glucose or pH level) are found. Although not entirely specific, indirect these parameters are codified in national guidelines (1) and commonly form the basis of entry criteria to studies recruiting from the pleural infection population.

The pattern of organisms implicated in pleural infection has evolved over the last few decades, with the most significant shift assumed to be associated with the widespread introduction of antibiotics. (13) Gram positive cocci, specifically the *Streptococcus anginosus* group in adults and *Strep pneumoniae* in children, are the primary culprits in community-acquired disease, although Gram-negatives (e.g. *Haemophilus influenzae*) and anaerobes are also found not infrequently. (16) Given this information, the choice of appropriate empirical antibiotics in pleural infection often differs subtly from that required in pneumonia. (1) Modern nucleic acid amplification techniques (NAAT) are beginning to reveal more about the pleural infection microbiome, suggesting a complexity and individuality which is not readily apparent using traditional culture and microscopy. (17) NAAT, however, is not yet in widespread clinical use and thus remains a tool largely reserved for research. The distinction between community-acquired disease and the less common healthcare-associated pleural infection, HAPI, (which accounts for around 15% of cases (12)) is an important one to make in deciding initial treatment. HAPI carries a significantly higher chance of morbidity and mortality and is caused by a different spectrum of bacteria, largely *Staphylococci* including MRSA, necessitating alternative antibiotic approaches. (12)

2.1.3 Medical management of pleural infection

As mentioned above, the early and rationalised use of empirical antibiotics forms the cornerstone of modern pleural infection management. (1) Patients also tend to be significantly catabolic and pro-thrombotic, and so require increased nutritional support alongside prophylactic anticoagulation during the presentation phase of their illness when they are most likely to be septic. (13) For those who have evidence of anything other than a very small effusion, (18) drainage of their collection is recommended – usually on at least a semi-urgent basis. (1) First line intervention for pleural infection usually involves insertion of an intercostal chest tube, under local anaesthetic, in the ward setting. The choice of drain size (diameter) has been a subject for historical debate. (19) Recent randomised evidence would suggest that wider tubes are more efficacious in some settings (such as malignant pleural effusions), (20) but this has not been supported in subgroup analysis of large pleural infection cohorts, where bigger drains appear only to be as effective as smaller ones, and at the expense of more pain. (7) Guidelines suggest that if a smaller drain is used, it should be flushed routinely to prevent occlusion with debris. (1) Extrapolating from this, pleural irrigation has been shown to improve outcomes in a randomised pilot study, (21) with this practice already considered routine in some European centres.

In some, effective drainage of fluid can be hindered by the presence of “septations” – strands of scar tissue which form a complex network of fluid pockets (“loculations”) within the pleural cavity. These patients may require treatment with newer, enzyme-based agents (specifically tissue plasminogen activator and deoxyribonuclease in combination) which are administered intrapleurally, and which have been shown to be efficacious enough to improve clinically-relevant outcomes in randomised trials. (7, 22, 23) This treatment, however, is expensive, laborious and needs to be given over an additional three day period. (7)

Should the approaches described above fail, then patients will often need thoracic surgery to enable debridement of the pleural cavity. Modern pleural infection surgery tends to be done using a minimally-invasive approach (video-assisted thoracoscopic surgery, VATS) and has excellent outcomes. (13) This technique, however, is reserved for those who are sufficiently fit to undergo general anaesthetic, a limitation which excludes many of the more elderly or frail patients who might fail to respond to medical treatment.

2.1.4 Medical thoracoscopy

Local anaesthetic thoracoscopy (LAT) is now an established investigation in pleural effusion. (24) It can be performed safely under conscious sedation, even as a day-case, and usually lasts around 45 minutes. It entails complete drainage and visual examination of the chest cavity using a small fiberoptic camera which is inserted via an intercostal port under local anaesthetic. During this time, there is usually opportunity to perform additional interventions such as parietal pleural biopsies, breakdown of septations, and in the case of suspected malignant disease, talc poudrage. (25) A chest drain is inserted at the end of the procedure to allow the lung to re-expand and to drain any residual fluid, with the size of tube determined by the diameter of the port inserted initially.

Rigid thoracoscopy is the commonest variant and can be performed using either a single- or dual-port approach. The stiffer device has the benefit of allowing larger biopsy size and more control over the whole of the scope, however it is sometimes limited in both the views it can provide and the areas of the chest which can be accessed for sampling. Flexible LAT (f-LAT) is a relatively novel technique which may address some of these issues, albeit at much greater cost and smaller biopsy size. (26, 27)

2.1.5 The role of medical thoracoscopy in pleural infection

In a few isolated centres on the European continent, the use of medical thoracoscopy for pleural infection is relatively common. However, there are currently only four published studies relating to this

practice: None of them are comparative or randomised; describe UK patients; include patient-subjective outcomes; look at rapidity of performing the procedure or duration of stay; or include flexible thoracoscopy. (28-31) A total of 191 patients are reported overall, the bulk coming from a paper by Brutsche et al, who undertook a multicentre retrospective review series of patients from three hospitals in Italy and Switzerland over a 14-year period. A third of this series' cases were performed as a result of failed initial tube drainage and half received post-procedure intrapleural fibrinolytics (albeit without DNase).

Despite their limitations, however, these studies would seem to support the hypothesis that medical thoracoscopy can be performed safely in this population, with complication rates akin to those seen in other thoracoscopy studies. Clinical outcomes were also encouraging, with a combined rate of 90% (172/191) of patients for avoiding surgery.

2.2 RATIONALE FOR CURRENT STUDY

2.2.1 The need for the SPIRIT trial

At the time of writing, UK thoracoscopy services are largely geared towards elective diagnostic procedures, with those who do undertake LAT for therapeutic purposes tending to do so only in the malignant population. In this group, the primary perceived benefit of choosing LAT over standard chest drain insertion is the ability to completely drain the pleural cavity and administer talc in a single procedure. Although logistically more challenging and slightly more demanding for patients, this approach is typically able to reduce the number of days spent in hospital such that there is likely to be a significant healthcare cost benefit. Given that patients with pleural infection can have average inpatient stays in excess of those with malignancy, the question of whether a similar reduction can be achieved by using LAT in this population is an important one. If either this, or an improvement in the need for step-up treatment, can be demonstrated then it could be argued that therapeutic medical thoracoscopy would represent a new standard of care for pleural infection in the UK, necessitating a shift in long-term service provision.

The most appropriate way to address the above is with a randomised controlled trial comparing the newer intervention to the current standard. However, before this can be attempted, it must be shown that there is enough flexibility in current set-ups to allow for urgent or semi-urgent thoracoscopy to be performed, as patients cannot be left with untreated pleural infection for extended periods of time. The SPIRIT trial will address this question directly, examining the feasibility of randomising patients to undergo either standard care or rapid medical thoracoscopy. This, along with the collection of basic

outcome and patient experience data, will hopefully allow the design and justification of a larger trial which is fully powered to evaluate those outcomes on a larger scale.

2.2.2 Patient and Public Involvement

The design of the SPIRIT trial incorporates valuable patient-subjective and qualitative components, as described in more detail below. To ensure that these are relevant, and to ensure the trial is run with a participant perspective in mind, the trial questions, the trial protocol, the semi-structured interview questions, and the trial steering committee all have patient involvement.

2.3 LAY SUMMARY

A pleural effusion is a collection of fluid in the space between the lung and the chest wall (the pleural cavity). It commonly occurs as a result of pneumonia and can cause significant breathlessness because the lung becomes compressed. In about 10% of cases, this fluid can itself go on to become infected, which increases the chances of someone becoming unwell enough to need surgery, or even dying. To reduce the chance of this happening, it is vital that the fluid is drained away completely as soon as possible after someone is diagnosed with pleural infection. This is usually done by inserting a small chest tube between the ribs and allowing the fluid to come out over period of about 24 hours. This treatment typically requires many days in hospital but is common and generally low risk.

Medical thoracoscopy is a common technique used to diagnose and drain effusions, although it is not routinely used for pleural infection in the UK as it tends to be reserved for those who are suspected of having cancer. It involves inserting a small camera between the ribs into the fluid and can be done under local anaesthetic. The procedure is very safe, but carries a slightly higher risk of complications than standard chest tube insertion. However, the main benefit of the procedure is that it can allow a patient to spend less time in hospital because the chest is drained completely all at once.

This study, the SPIRIT trial, is designed to see if a group of UK hospitals are able to safely offer medical thoracoscopy to patients with pleural infection. It will recruit 30 patients from 7 UK hospitals over a year and will randomly allocate half of them to undergo thoracoscopy and half to the standard chest drain. Over 3 months of follow up, we shall also examine how the treatment affects patients themselves, and whether it is effective at reducing patients' time in hospital or their need for surgery.

3. STUDY OBJECTIVES

3.1 PRIMARY RESEARCH QUESTION

Is it feasible and acceptable to randomise 30 patients to undergo either medical thoracoscopy or standard chest tube insertion for the treatment of pleural infection requiring drainage, and to deliver the trial protocol to a UK population of patients?

3.2 SECONDARY RESEARCH QUESTIONS

Regarding those patients who are treated with medical thoracoscopy for pleural infection:

1. Does this approach reduce the time spent in hospital compared to standard treatment?
2. Does this approach affect the need for “step-up” therapy?
3. Does this approach affect lung function over the weeks following treatment?
4. Does this approach affect pleural effusion size or overall complexity, measured radiologically over time?
5. Does this approach affect the microbiological yield in comparison to standard sampling techniques?
6. How does using this approach affect overall costs compared to standard treatment?
7. How does using this approach affect patients’ subjective quality of life?
8. What are patients’ experiences of trial involvement and of the procedures themselves?

4. STUDY DESIGN

4.1 TRIAL TYPE

The SPIRIT trial is an open-label, randomised, feasibility study aiming to gather preliminary information on whether there is a role for medical thoracoscopy in the management of pleural infection requiring chest drainage.

The trial allocates participants to receive one of two treatments which are both freely available and routinely used throughout the NHS. There are no novel devices or investigational medicinal products incorporated in the trial design. As such, SPIRIT will be classified as a non-CTIMP study for the purposes of regulatory approvals and adverse event reporting.

A subset of participants will also be invited to undergo qualitative, semi-structured interviews to better understand their experiences of pleural infection and trial involvement.

4.2 TARGET POPULATION

The target population for the SPIRIT trial are those patients who have been diagnosed with a pleural infection requiring intercostal drainage, and who meet the inclusion and exclusion criteria as described in sections 5.2 and 5.3.

The study will aim to randomise 30 patients (in a 1:1 ratio) to either the control or intervention arm, with up to 10 patients from each undergoing semi-structured interview.

4.3 STUDY OUTCOME MEASURES

4.3.1 Primary outcome

The primary outcome is the feasibility of being able to recruit patients and randomise them to undergo medical thoracoscopy for pleural infection, and of being able to deliver the trial protocol. This will be assessed as follows:

- Pre-randomisation:
 - The total number of pre-screen and screen failures, and the proportions of each compared to the overall number assessed for trial involvement
- Post-randomisation:
 - The total number of allocation failures in both arms of the study

Pre-screen, screen and allocation failures are defined in sections 5.1 and 6.3.3.

4.3.2 Secondary outcomes

- Duration of stay due to pleural infection, as measured by the number of nights in hospital between enrolment and being recorded as medically fit for discharge
- Total inpatient time, as measured by the number of nights in hospital between enrolment and the end of the 90-day post-procedure follow-up period
- Need for step-up therapy, as measured by the difference in proportion of patients requiring intrapleural fibrinolytic therapy or referral for surgical debridement
- All-cause mortality, as measured by the number of patients remaining alive at days 30 and 90 post procedure
- Degree of pleural fluid septation, as measured by the change in bedside thoracic ultrasound septation score from baseline to follow-up days 1, 3, 7, 30 and 90 post procedure
- Pleural effusion size, as measured by the change in radiographic hemithorax opacification from enrolment to discharge, and days 1, 30 and 90 post procedure
- Microbiological yield, as measured by the difference in proportion with positive culture or stain between the control and intervention arms
- Total costs of interventions, as measured by the difference in total cost of treatment for pleural infection (from enrolment to being medically fit for discharge) between two arms
- Quality of life, as measured by the change in EQ-5D subjective health score from baseline to days 30 and 90 post procedure
- Patient experiences, as determined by exploring patients' perceptions and experiences of interventions before and after their procedure through semi-structured interviews

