6.3.6 Referral for thoracic surgery

For some patients, in the event of the failure of the medical treatments described above, a referral for thoracic surgery (e.g. VATS debridement) may become necessary. As before, the use of this option is at the discretion of the treating physician and may be considered in any patient at any time during their treatment course.

The need for referral for rescue surgery will be recorded as a trial outcome measure.

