6.3.7 Discharge

The timing of a patient's discharge remains at the discretion of the treating physician. For the purposes of the trial analysis, both the date when a patient is made medically fit for discharge and the date of their actual discharge will be recorded.

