7.1.3 Secondary endpoint analysis

Quantitative secondary endpoints will be analysed on both an intention-to-treat and, separately, a per protocol basis. Results will be presented in terms of between-group differences in either means or medians, with associated 95% confidence intervals.

Categorical data will be analysed using the Chi-squared approach (or Fisher's exact test where appropriate). Ordinal data will be analysed using the Mann Whitney U test or an independent sample t-test. Survival (time-to-event) data will be presented in the form of Kaplan-Meier curves and analysed using the Logrank test (with Cox proportional hazards analysis also performed).

The semi-structured interview component of the study will be analysed using a recognised qualitative approach, such as framework analysis, thematic analysis, or a combination of the two.

Analysis of anonymised radiological images will be performed by two clinicians, who will be blind to treatment allocation. Assessment of pleural effusion size will be performed using a recognised and previously published method. (7)

The comparison of treatment costs between randomisation and being medically fit for discharge will be performed from the perspective of the UK National Health Service, with prices of interventions or treatments being referenced from standard resources.

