8.3 EXPECTED ADVERSE EVENTS

The following are considered to be expected in the context of patients suffering with pleural infection and who require an intervention for fluid drainage.

- Chest pain, or discomfort around procedure site (unless not improving or remains unresponsive to analgesia)
- Bleeding associated with trial procedure (unless causing haemodynamic compromise, requiring transfusion, or requiring intervention to achieve haemostasis)
- Surgical emphysema (unless requiring surgical referral or causing airway compromise)
- Subcutaneous infection related to thoracoscopy or drain insertion, (unless unresponsive to antibiotic therapy)
- Chest drain falling out, becoming dislodged or becoming blocked
- Pneumothorax or evidence of non-expandable lung following chest drain insertion or thoracoscopy (unless requiring surgical intervention)
- Hospital admission, elective procedure or surgery, disability, incapacity or death due to underlying or pre-existing condition
- Delay in planned discharge date (unless due to a complication directly related to a trial procedure)
- Readmission to hospital or need for thoracic surgery due to pleural infection or pneumonia
- Hypotension or tachycardia due to sepsis requiring intravenous fluid support alone
- Hypothermia or hyperthermia due to sepsis, within the range $\geq 34.0^{\circ}\text{C}$ to $\leq 39.4^{\circ}\text{C}$
- A reaction to an administered medication (unless not described in the current version of the British National Formulary (BNF))

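### The cost outcome closes when the patient is recorded as medically fit, so later treatment of the same pleural infection is not costed, although the research question is about overall costs

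*Protocol*

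**What the plan says.** Protocol section 3.2 poses the cost question without a time limit: "How does using this approach affect overall costs compared to standard treatment".

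Section 4.3.2 then defines the outcome as the difference in "total cost of treatment for pleural infection (from enrolment to being medically fit for discharge) between two arms". Section 7.1.3 describes the "comparison of treatment costs between randomisation and being medically fit for discharge". The two sections start the clock at different events, but section 6.1.1 puts consent and randomisation on the same day, so that difference is small. Both stop it at the same event.

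Infection-related stay in section 4.3.2 has the same stop: the "number of nights in hospital between enrolment and being recorded as medically fit for discharge". Two neighbouring outcomes in that section reach further. Total inpatient time counts nights to the end of the 90-day follow-up, whatever the cause. Step-up therapy counts enzyme treatment or surgical referral with no stated time limit.

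Section 6.3.7 leaves the timing of discharge to the treating physician and says that "both the date when a patient is made medically fit for discharge and the date of their actual discharge will be recorded". It mentions one such date and gives no rule for a second one after a readmission.

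Other sections foresee treatment after that date. Section 8.3 lists among the expected events "Readmission to hospital or need for thoracic surgery due to pleural infection or pneumonia". Section 6.3.6 says that surgical referral "may be considered in any patient at any time during their treatment course". Section 6.3.8 schedules follow-up visits at days 30 and 90.

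**The concern.** An early discharge can be followed by treatment failure. A return to hospital for the same infection, perhaps with enzyme therapy or surgery, is the event most likely to cancel the saving from a short index stay. Under the stated window, that later care falls outside the cost comparison. An arm that discharged earlier and readmitted more would look cheaper than it is.

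The date that closes the window is set by clinicians who know the allocation, since the trial is open label (section 6.2.3). The same operation is costed if it happens before that date and free if it happens after.

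Cost and stay are part of the case for a later trial. Section 2.2.1 points to a likely cost benefit from shorter stays in malignant disease and asks whether a similar reduction in stay can be had in infection. It hopes that the outcome data will help to design and justify a larger study. Section 9.3 ties that larger study to a shorter in-hospital treatment being supported by the results. A cost figure that leaves out late failure would be a poor input to that decision.

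**Working it through.** **The plan's own figure.** Section 7.1.1 expects 150 patients in a year and one in five recruited: 150 × 1/5 = 30, as stated. At 1:1 this is about 15 per arm. The protocol gives no readmission rate, readmission length or unit price.

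**Which outcome sees care after medically fit**

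| Event after the medically-fit date | Infection-related stay | Total inpatient time | Step-up therapy | Cost |
|---|---|---|---|---|
| Nights of a readmission for the infection | no | yes, all-cause to day 90 | – | no |
| Enzyme therapy on readmission | – | nights only | yes | no |
| Late surgical referral and surgery | – | nights only | yes (referral) | no |

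The cost column has no entry, so nothing else in the plan makes up for the cut-off. The nights are recovered in the second column.

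**Two invented patients with the same burden.** Patient A is medically fit and goes home after 5 nights, then is readmitted for 10 nights with surgery. Patient B has one 15-night admission with the same surgery and is medically fit at its end.

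| | A | B |
|---|---|---|
| Infection-related stay | 5 | 15 |
| Total inpatient time | 5 + 10 = 15 | 15 |
| Step-up therapy | yes | yes |
| Nights costed | 5 | 15 |
| Surgery costed | no | yes |

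Total inpatient time and step-up therapy treat the two alike. Cost does not.

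**Illustrative size (assumed inputs).** The shift in the between-arm mean is (extra readmitted patients in one arm × nights each) / 15.

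- 1 patient, 5 nights: 5/15 = 0.33 nights
- 1 patient, 12 nights: 12/15 = 0.8 nights
- 3 patients, 14 nights: 42/15 = 2.8 nights

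These are bed-days per patient missing from the cost difference; any late surgery comes on top. The chance that at least one of 30 patients is readmitted, at an assumed risk r, is 1 − (1 − r)^30: 79% at r = 5%, 96% at 10%, and over 99% at 20%. If readmission risk is in that range, the gap would probably touch at least one patient.

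**The case against.** The strongest defence concerns stay. A reader might infer that readmissions for infection vanish from the trial's account of time in hospital. They do not: total inpatient time, the next outcome in the same list, counts every night to day 90. It is all-cause, but in a randomised comparison unrelated nights should mainly add noise. Ending the other stay measure at medically fit also has a purpose, since it leaves out non-clinical discharge delay. This stands, and it reduces the stay part to a matter of labelling.

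Other inferences also go too far.

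- That the window closes at the first medically-fit date is the natural reading of section 6.3.7, but the text does not say first. A statistical analysis plan, not shown here, might settle a second date. The end point itself is fixed in the protocol, in two sections.
- The pooled series in section 2.1.5 (172 of 191 avoided surgery, so 19/191 = 9.9% did not) might be read as a rate of uncosted surgery. It is not one. A third of the largest series followed failed tube drainage, whereas this trial tests first-line use, and nothing says that the surgery came after discharge.
- Section 2.2.1 might be read as using this trial's figures to change services. It makes that change depend on a demonstrated benefit, for which it asks for a later randomised trial.
- No document indicates which arm would have more readmissions.

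It can also be said that the cost window is stated openly and could simply be renamed an index-episode cost. That would make the label accurate but would leave question 6 in section 3.2 unanswered.

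**Conclusion.** The point holds for cost. Sections 4.3.2 and 7.1.3 fix an end point that leaves later treatment of the same infection uncosted, while the question is about overall costs and the protocol itself expects such treatment within a follow-up of 90 days. The omission favours whichever arm discharges earlier and readmits more. For infection-related stay the same cut-off is minor, because neighbouring outcomes capture the readmission nights and the late referrals.

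The size is unknown. The shift of 0.33 to 2.8 nights per patient rests wholly on assumed readmission numbers and lengths, and no money value can be given without prices. Both outcomes are secondary in a 30-patient feasibility study. The success rules in section 7.1.2 use only pre-screen, screen and allocation failures, so the primary outcome is untouched, as is the sample size. The change is worth making because the cost result is meant to inform the next trial.

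**What to change.** - In sections 4.3.2 and 7.1.3, run the cost window from enrolment to day 90. Include readmissions, enzyme therapy and surgery for pleural infection, and care after transfer to another hospital. Use the same start event in both sections.
- Keep the cost to medically fit as a supporting index-episode result.
- Label the existing infection-related stay as an index-episode measure, to be read alongside total inpatient time.
- Add one eCRF item giving the cause of each readmission. Because that is an open-label judgement, show an all-cause version of the day-90 cost as well.

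The cost is modest. Nights to day 90 are already needed for total inpatient time, and under section 8.2 adverse events go on the eCRF, with expected serious events still recorded. The extra work is to collect and price some later resource items. Care after transfer needs the most effort, because the scheduled inpatient recording in section 6.3.4 stops at discharge or transfer. No change to treatment or to the number of patients is required.
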